### **3 Study Implementation**

#### **3.1 Study Design**

The primary objective of this study is to determine whether pulmonary metastasectomy and treatment with saracatinib, versus pulmonary metastasectomy and treatment with placebo, results in an increase in progression free survival. A secondary objective is to determine whether pulmonary metastasectomy and treatment with saracatinib, versus pulmonary metastasectomy and treatment with placebo, results in an increase in overall survival. Patients will be eligible for the study following the histological verification of recurrent osteosarcoma. Patients will be stratified based on the number of recurrences (FIRST versus SECOND versus THIRD or MORE) and the number of recurrent nodules (ONE or TWO versus THREE or MORE).

Randomization will occur following complete resection of all lung nodules and the histological verification of recurrent osteosarcoma.

Patients who are randomized to the saracatinib arm will receive saracatinib, 175 mg, orally, once daily, for a 28-day cycle, with no breaks between cycles. The total duration of treatment with saracatinib will be **thirteen 28-day cycles** (364 days total). Patients will receive one 125 mg tablet (9.5 mm diameter) and one 50 mg tablet (7 mm diameter).

Patients who are randomized to the placebo arm will receive placebo, orally, once daily, for a 28-day cycle, with no breaks between cycles. The total duration of treatment with placebo will be **thirteen 28-day cycles** (364 days total). Patients will receive one 9.5 mm tablet and one 7 mm tablet. These tablets will be indistinguishable from saracatinib.

Patients who recur in the lung while on-study and who are thought to be completely resectable will be unblinded. Those patients who were receiving placebo will be offered the opportunity to undergo additional surgical resection, followed by treatment with Saracatinib. If fully resected, they will then begin oral therapy with saracatinib. Saracatinib will be administered as a once daily, oral dose of 175 mg, for a 28-day cycle, with no breaks between cycles. The duration of treatment with saracatinib will be thirteen 28-daycycles (364 days total).

Patients will be followed for the duration that this study is open. If accrual rates proceed as projected, the total duration of this study will be six years.

## **3.2 Treatment Administration**

### **3.2.1 Administration and Commencement of Oral Therapy**

Patients will receive two bottles that contain either saracatinib or placebo. One bottle will contain 125 mg tablets (or a similar placebo tablet) and the other bottle will contain 50 mg tablets (or a similar placebo tablet).

Patients will take one 125 mg tablet and one 50 mg tablet, once every day, for the duration of the trial. The tablets can be taken at any time of the day, with or without food. See Sections 4.5, 4.6 and 4.7 for a list of medications and food products that should be avoided while on study. Patients will also be asked to keep a daily diary of the time and dose of the drug ingested. (see Appendix B).

There are three possibilities for disease burden in our study population. First: patients who had very few nodules at recurrence, may have had resection of all of the nodules at the time of the biopsy. Second: patients who had biopsy of one nodule and require one additional surgery for complete resection of any remaining nodules. Third: patients who had biopsy of one nodule who have bilateral disease that requires a staged thorocotomy to obtain surgical remission. The timing of enrollment, randomization and commencement of oral therapy, with either saracatinib or placebo, is detailed below for all three of these possibilities.

### 3.2.2 Distinction between Enrollment and Randomization

This protocol distinguishes between enrollment and randomization. Patients with suspected or confirmed recurrence of osteosarcoma localized to the lung will be enrolled in the study following informed consent. This allows for the collection of tumor samples (for patients with suspected recurrence of osteosarcoma who have not yet undergone surgical resection), and their subsequent examination, which is an important objective in this protocol. However, randomization will not occur until the patient has had complete surgical resection of all recurrent tumor nodules.

There will be several patients who are deemed fully resectable based on a CT scan. In a few cases, at the time of definitive surgery, the surgeon will find more tumor burden than was expected. At that point, if total tumor resection is not possible, the procedure may be stopped due to high morbidity risk.

Patients who have been enrolled in the study, but subsequently are not fully resected of tumor will not be randomized and therefore, they will not be included in any efficacy or toxicity studies. However, their tumor samples can still be analyzed (see Section 3.6.1 and Operations Manual). These patients will be followed for overall survival only. Their primary oncologist will manage their medical care. The continued monitoring for overall survival on this study does not preclude them from any other trials or treatments that these patients will undergo.

### 3.2.3 Regimen for Patients Who Have Been Fully Resected

Patients who had resection of all tumor nodules at the time of their biopsy will be eligible for randomization after definitive histological diagnosis of recurrent osteosarcoma. Once the treating physician decides that the patient is able to tolerate oral therapy, the patient will be randomized to either the saracatinib arm or the placebo arm. Following randomization, tablets will be dispensed by the hospital pharmacy.

Cycle 1 Day 1 must commence no later than 6 weeks after the time of the definitive metastasectomy. Patients who cannot commence oral therapy within these time frames will be removed from the study.

### 3.2.4 Regimen for Patients Who Require Definitive Resection

Patients who underwent biopsy of a nodule but have remaining nodules will be eligible for randomization after definitive histological diagnosis of recurrent osteosarcoma. These patients should undergo definitive pulmonary metastasectomy as soon as possible. Following definitive surgical resection of all metastatic nodules, and once the treating physician decides that the patient is able to tolerate oral therapy, the patient will be randomized to either the saracatinib arm or the placebo arm. Following randomization, tablets will be dispensed by the hospital pharmacy.

Cycle 1 Day 1 must commence no later than 6 weeks after the time of the definitive metastasectomy. Patients who cannot commence oral therapy within these time frames will be removed from the study.

Biological studies to determine the etiology of recurrent osteosarcoma are an important component of this protocol. Prior to metastasectomy, every attempt should be made to insure that the tumor sample is handled properly, so that all of the biological studies can be performed (see Sections 3.6.1 and Operations Manual).

### 3.2.5 Regimen for Patients Who Require Staged Thoracotomies

Patients with extensive bilateral disease that requires staged thoracotomies will be eligible for enrollment. These patients should undergo resection of one side as soon as possible. Resection of the other side should be performed at a time determined by the surgical oncologist. Following definitive surgical resection of all metastatic nodules, histologic confirmation of osteosarcoma, and once the treating physician decides that the patient is able to tolerate oral therapy, the patient will be randomized to either the saracatinib arm or the placebo arm. Following randomization, tablets will be dispensed by the hospital pharmacy.

Cycle 1 Day 1 must commence no later than 6 weeks after the time of the definitive metastasectomy. This will allow for the resolution of any complications that may arise as a result of the procedure, prior to administration of oral therapy. Patients who cannot commence oral therapy within these time frames will be removed from the study.

Biological studies to determine the etiology of recurrent osteosarcoma are an important component of this protocol. Prior to BOTH surgeries, every attempt should be made to insure that the tumor sample is handled properly, so that all of the biological studies can be performed (see Sections 3.6.1 and Operations Manual).

### 3.2.6 Cross-over Regimen for Patients Who Recur in the Lung While On-Study

Patients who recur in the lung while on study, and who are thought to be amenable to complete surgical resection of the recurrent tumor will be unblinded. Those patients who were receiving placebo will then have the option of undergoing surgical resection; if fully resected they will be given the option to begin oral therapy with Saracatinib.

Saracatinib will be administered as a once daily, oral dose of 175 mg, for a 28-day cycle, with no breaks between cycles. The duration of treatment with saracatinib will be thirteen 28-day cycles (364 days total). Cycle 1 Day 1 must commence no later than 6 weeks after the time of the definitive metastasectomy. Patients who cannot commence oral therapy within 6 weeks will be removed from the study.

Biological studies to determine the etiology of recurrent osteosarcoma are an important component of this protocol. Prior to metastasectomy, every attempt should be made to

insure that the tumor sample is handled properly, so that all of the biological studies can be performed (see Sections 3.6.1 and Operations Manual).

Patients who recur in locations other than the lung while on-study will be taken off study and will not be unblinded.

### **3.3 Treatment Modifications**

#### **3.3.1 Dose Modification Criteria**

Dose reductions should be applied if any of the following toxicities occur

##### Hematological

- Any CTCAEv3 grade 4 hematological toxicity of any duration (With the exception of CTCAEv3 grade 4 neutropenia  $\leq 6$  days duration. For CTCAEv3 grade 4 neutropenia  $\leq 6$  days duration, oral therapy will be held until the neutropenia recovers to CTCAEv3 grade 1 or less, at which time oral therapy will resume at the same dose)
- Febrile neutropenia (CTCAEv3 grade 3 neutropenia with temperature  $\geq 38.5^{\circ}\text{C}$  or CTCAEv3 grade 4 neutropenia with temperature  $\geq 38.0^{\circ}\text{C}$ )
- CTCAEv3 grade  $\geq 3$  neutropenia requiring hospitalization
- CTCAEv3 grade  $\geq 3$  thrombocytopenia associated with non-traumatic bleeding (with the exception of patients on therapeutic anti-coagulation)

##### Non-Hematological

- Any CTCAEv3 grade  $\geq 3$ , non-hematological toxicity (with the exception of alopecia, nausea and vomiting)
- CTCAEv3 grade  $\geq 3$ , hypophosphatemia (see section 3.3.3 for modified dose reduction schema)
- CTCAEv3 grade  $\geq 3$  nausea or CTCAEv3 grade  $\geq 3$  vomiting, lasting  $>24$  hours despite IV fluids, anti-emetic therapy and adequate supportive care
- Chronic CTCAEv3 grade 2 nausea or vomiting

In the event of any toxicity, of any grade, that the treating physician suspects is due to disease progression, re-evaluation of tumor status is indicated, irrespective of scheduled clinic visits.

### 3.3.2 Dose Reduction of Oral Therapy

If a patient experiences any of the toxicities defined in section 3.3.1, or another unacceptable toxicity occurs, and the investigator considers that the event is related to the study drug, oral therapy will be stopped for a maximum of 21 days, and supportive therapy will be administered as required. If the toxicity resolves or reverts to a CTCAEv3 grade 0 or grade 1 or to the baseline (pre-study) grade within 21 days of onset, oral therapy will be restarted at a lower dose as follows:

If a patient is currently taking 175 mg, the lower dose will be 125 mg.

If a patient is currently taking 125 mg, the lower dose will be 100 mg.

A maximum of two dose decreases, for any individual patient, can be made during the study period, down to the lowest dose of 100 mg of saracatinib or placebo.

If a patient experiences any of the toxicities defined in Section 3.3.1, or another unacceptable toxicity occurs, while taking 100 mg, then the patient must be withdrawn from the study. For all patients who experience any of the toxicities defined in Section 3.3.1, or another unacceptable toxicity occurs during the study, if the toxicity does not resolve to CTCAEv3 grade 0 or grade 1 or to the baseline (pre-study) grade within 21 days of onset, then the patient must be withdrawn from the study. Patients will continue to be monitored until the toxicity has resolved.

Patients will continue to be monitored for overall survival for the duration of the study. If patients have toxicity that requires their removal from the study prior to ascertainment of disease progression, then these patients will be considered treatment failures in the time to treatment failure analysis and the duration of total treatment will be included in the time to treatment failure. However, for the progression free survival analysis, withdrawals due to toxicity will be censored, as the subject has not progressed.

### 3.3.3 Dose Reduction of Oral Therapy for Hypophosphatemia

Hypophosphatemia may be encountered for reasons that are unrelated to the study drug, such as vitamin D deficiency. Prior to beginning oral therapy, treating physicians should obtain a full work-up to evaluate low or borderline low levels of phosphorus. In addition, additional time to allow hypophosphatemia to normalize will be allowed.

If a patient experiences CTCAEv3 grade 3 hypophosphatemia, dose reduction will occur as per section 3.3.2. However, oral therapy may be stopped for a maximum of 35 days, and supportive therapy will be administered as required. If the toxicity resolves or reverts to a CTCAEv3 grade 0 or grade 1 or to baseline (pre-study) grade within 35 days of onset, oral therapy will be restarted at a lower dose. If the toxicity does not resolve to CTCAEv3 grade 0 or grade 1 or to baseline within 35 days of onset, then the patient must be withdrawn from the study.

### 3.4 On Study Evaluations

Treatment with saracatinib or placebo will be given for **thirteen 28-day cycles (364 days)**. Patients will be required to return for routine follow-up visits as indicated in the chart below.

For patients enrolled on this study, evaluations must be administered at the study site for the pre-treatment evaluation and for the 3, 6, 9, and 13 cycle visits. For all other study evaluations (including specified follow up evaluations), the investigator may determine in the best interest of the patient that those evaluations may be safely conducted at a local, competent, referring oncologist's office. The institutional principal investigator is responsible for the timely and accurate reporting of data to the SARC Operations Center.

Treatment Evaluations (also available in table form, see Appendix A)

All treatment evaluations/procedures should be performed within a +/- 7 day window, with the exception of week 1 and week 3-4 which should be done within +/- 3 day window.

Pre-treatment	history, physical, vital signs, laboratory tests
Day 1	BEGIN oral therapy of saracatinib or placebo
Week 1	history, physical, vital signs, laboratory tests *
Week 3-4	history, physical, vital signs, laboratory tests * thoracic CT */**
Week 6-8	history, physical, vital signs, laboratory tests * thoracic CT */**
Week 9	history, physical, vital signs, laboratory tests *
3 months/Cycle 3	history, physical, vital signs, laboratory tests thoracic CT EKG ***
4 months/Cycle 4	history, physical, vital signs, laboratory tests *
5 months/Cycle 5	history, physical, vital signs, laboratory tests *
6 months/Cycle 6	history, physical, vital signs, laboratory tests thoracic CT
7 months/Cycle 7	history, physical, vital signs, laboratory tests *
8 months/Cycle 8	history, physical, vital signs, laboratory tests *
9 months/Cycle 9	history, physical, vital signs, laboratory tests thoracic CT
10 months/Cycle 10	history, physical, vital signs, laboratory tests *
11 months/Cycle 11	history, physical, vital signs, laboratory tests *
12 months/Cycle 12	history, physical, vital signs, laboratory tests
13 months/Cycle 13	perform thoracic CT and bone scan within 14 days after the last dose DISCONTINUE oral therapy of saracatinib or placebo after thirteen 28-day cycles (364 days of therapy) *****
15 months	history, physical, vital signs *
18 months	history, physical, vital signs, laboratory tests

	thoracic CT
21 months	history, physical, vital signs *
24 months	history, physical, vital signs, laboratory tests thoracic CT
30 months	history, physical, vital signs *
36 months	history, physical, vital signs, laboratory tests thoracic CT

Laboratory tests are as follows:

- white blood cell count with differential
- hemoglobin and hematocrit
- platelet count
- sodium, potassium, chloride, bicarbonate, blood urea nitrogen, creatinine, glucose
- calcium, magnesium, phosphorus
- ALT, AST, total bilirubin,
- alkaline phosphatase, lactate dehydrogenase, total protein, albumin

\* At the discretion of the treating physician, these visits do not need to be performed at the study center. However, a document containing the interim history, physical examination, weight and height, vital signs, laboratory tests, and CT scan results when appropriate, must be sent to the treating physician at the study center as soon as they are available.

\*\* The purpose of the two additional thoracic CT scans is to monitor for interstitial lung disease, which has been seen in 2% of patients taking saracatinib. If there is any suspicion of interstitial lung disease on any CT scan, the patient must undergo high-resolution CT imaging to exclude interstitial lung disease. Any evidence of interstitial lung disease will lead to removal of the patient from the study (defined in the Exclusion Criteria in Section 2.1.2.f). The suggested parameters for the high-resolution thoracic CT scan are as follows: position (supine), slice thickness ( $\leq 1.25$  mm), slice spacing (10 mm), start location (10 mm below the apices), end location (10 mm above the costophrenic angles).

\*\*\* Previous studies have not demonstrated prolonged QTc intervals in patients treated with saracatinib. A 12-lead EKG should be obtained after the patient has rested in a supine position for at least five minutes. The treating physician should review the EKG. Any abnormality of clinical significance should result in medical management of the patient as clinically indicated. The abnormality should be reported as an adverse event or a serious adverse event (see Section 7.2).

\*\*\*\* Saracatinib or placebo will be discontinued after thirteen 28-day cycles (364 days) of therapy.

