A monotherapy study has also been performed in 81 patients with advanced solid malignancies refractory to or unsuitable for standard therapy, or for whom no standard therapy existed. In this study, patients received saracatinib continuously, every day, without any breaks between cycles. This was a two-part, Phase 1, open-label, multi-center study. Part A had the aim of establishing the appropriate dose of saracatinib monotherapy for use in future studies of patients with advanced solid malignancies. Part B had the aim of evaluating the effect of saracatinib on c-Src kinase activity in human cancers over a range of doses. In Part A, 30 patients received daily doses of saracatinib from 60 mg to 250 mg. The duration of therapy ranged from 6 to 150 days, with a median of 23 days. Dose limiting toxicity (DLT) was defined using the Common Terminology Criteria for Adverse Events (CTCAE) Version 3 (<http://ctep.cancer.gov/forms/CTCAEv3.pdf>). Part A defined the MTD in the patient population who participated as 175 mg daily. DLTs at 250 mg were as follows: grade 5 septic shock with grade 3 renal failure, grade 3 fatigue and grade 3 leucopenia. DLTs at 200 mg were grade 3 febrile neutropenia and grade 3 dyspnea. In Part B, 51 patients were randomized in a parallel-group cohort-expansion phase of three doses of saracatinib previously declared tolerable in Part A. In Part B of the study, 16 patients received 50 mg saracatinib daily, 16 patients received 125 mg saracatinib daily and 19 patients received 175 mg saracatinib daily. The duration of therapy ranged from 7 to 210 days, with a median of 25 days.

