A dose related effect of saracatinib on neutrophil and platelet counts in healthy volunteers has been identified. These effects are seen following multiple dosing (up to 14 days has been evaluated in healthy volunteer studies) but were not apparent following single dose administrations of up to 1000 mg. In all cases within healthy volunteers, neutrophil and platelets counts returned to near baseline values within a period of time that drug levels may be considered pharmacologically relevant (within 3 days,  $t_{1/2}$  of saracatinib is 40 hours) or during therapy. Moderate declines in neutrophil counts were also observed in patients with advanced cancer, with a nadir at 10 to 25 days of continuous saracatinib treatment. However, the majority of these declines were not clinically significant, with counts recovering without the need for dose interruption or the addition of supportive care.

Declines in hemoglobin levels were observed in patients with advanced cancer. The majority of these declines were of little clinical significance with counts recovering without the need for dose interruption or dose reduction. These declines occurred in patients with multiple confounding factors (treatment with multiple cytotoxic agents, administration of non-steroidal anti-inflammatory drugs for analgesia, previous history of peptic ulcer disease, prior blood transfusions to permit entry into the study), thus making evaluation difficult. No overt effect on platelet values has been identified in patients with advanced cancer. No evidence of cumulative hematological toxicity has been observed in either healthy volunteers or patients with advanced cancer.

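### No scheduled blood count is guaranteed within the protocol's own neutrophil nadir range of days 10 to 25; capping the week 3-4 draw at day 25 would guarantee one

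*Combined protocol and SAP*

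**What the plan says.** Section 1.2.8 reports moderate neutrophil declines in patients with advanced cancer, "with a nadir at 10 to 25 days of continuous saracatinib treatment". It adds that "the majority of these declines were not clinically significant, with counts recovering without the need for dose interruption".

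Section 3.4 lists laboratory tests, which include a "white blood cell count with differential", at week 1, week 3-4 and week 6-8, with none scheduled in between. The general rule on timing is "All treatment evaluations/procedures should be performed within a +/- 7 day window". The two earliest visits have a tighter tolerance: "with the exception of week 1 and week 3-4 which should be done within +/- 3 day window". Appendix A has the same visits, and its footnotes g and h give 3 days for both the early and the later ones.

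Section 3.3.1 (Hematological) makes dosing depend on the count. Grade 4 neutropenia of 6 days or less leads to a hold until recovery, "at which time oral therapy will resume at the same dose"; a longer episode leads to a dose reduction. Febrile neutropenia and grade 3 or higher "neutropenia requiring hospitalization" are separate triggers.

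**The concern.** The protocol states when neutrophils are expected to be lowest and writes a dose rule that needs a neutrophil count, but its schedule does not ensure that a count is taken then. A patient with asymptomatic grade 4 neutropenia has no symptom to prompt an extra draw, so a scheduled count is the only stated way to see it. If the count misses the episode, the hold or reduction is not triggered and the event is not recorded. The same applies to cross-over patients newly starting saracatinib (section 3.2.6). This is a point about safety monitoring only.

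**Working it through.** **Inputs.** Nadir range: days 10 to 25 (section 1.2.8). Week 1 and week 3-4 tolerance: 3 days (section 3.4, Appendix A). Week 6-8 tolerance: 7 days (section 3.4) or 3 days (Appendix A). The documents do not say which days the week labels mean, so several readings are tried. The plan states no figure of its own to reproduce.

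**Step 1: permitted draw days.**
- Week 1 as day 7 ± 3: days 4 to 10. Only day 10 lies in the range, so 6 of 7 days miss.
- Week 3-4 as days 21 to 28, ± 3: days 18 to 31. Days 26 to 31 miss, so 6 of 14 miss and 8 of 14 fall inside.
- Week 3-4 as days 15 to 28, ± 3: days 12 to 31. Again days 26 to 31 miss, so 6 of 20 miss and 14 of 20 fall inside.
- Week 3-4 kept to nominal days 15 to 28 with no tolerance: days 26 to 28 miss, so 3 of 14. The broad label causes the gap as much as the tolerance does.
- Week 6-8: if week 6 starts on day 36, the earliest draw is 36 − 7 = day 29, or 36 − 3 = day 33. Neither is in the range.

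**Step 2: permitted day pairs with no count in days 10 to 25.** Missing pairs = (week 1 days that miss) × (week 3-4 days that miss).

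| Week 3-4 draw days | Missing pairs now | After cap at day 25 |
|---|---|---|
| 18 to 31 | 6 × 6 = 36 of 7 × 14 = 98 | 0 |
| 12 to 31 | 6 × 6 = 36 of 7 × 20 = 140 | 0 |
| 15 to 28 (nominal) | 6 × 3 = 18 of 7 × 14 = 98 | 0 |

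Two further readings agree. Taking week w as day 7w + 1 gives 35 of 98. Calendar weeks for both visits (week 1 draw on days 1 to 10, week 3-4 draw on days 12 to 31) gives 54 of 200. Both fall to 0 after the cap. The pair of days 7 and 28 is compliant, and misses, under every one of these readings. These are counts of permitted pairs, not probabilities.

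The cap has to be the last permitted day. If only the target day were capped at 25 and 3 days were still added, draws on days 26 to 28 would remain compliant. Then 18 pairs (week w as day 7w), 15 (day 7w + 1) or 27 (calendar weeks for both visits) would still miss.

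**Step 3: illustration of detection.** Assume the nadir day is uniform on 10 to 25, the week 1 draw is uniform on 4 to 10, and the week 3-4 draw is uniform on its permitted days. Assume also that a grade 4 episode of length d is centred on the nadir, and that it is seen if either draw lies within d/2 of the nadir. Only the nadir range comes from the documents. Simulation with 4,000,000 draws gives, now to capped:

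| Week 3-4 draw days | d = 6 | d = 10 | d = 14 |
|---|---|---|---|
| 18 to 31 | 27% to 41% | 50% to 68% | 74% to 91% |
| 12 to 31 | 32% to 42% | 55% to 67% | 76% to 86% |
| 15 to 28 | 36% to 42% | 62% to 70% | 84% to 91% |

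The gain is about 6 to 14, 7 to 19 and 6 to 17 percentage points respectively. It is smallest when draws already keep to nominal days. Even after the cap, at least 58% of 6-day episodes would go unseen.

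**The case against.** **The upper limit of day 25 may be soft.** In the Phase I study the median time on treatment was 23 days in Part A and 25 days in Part B (section 1.2.8), so the limit may partly reflect short exposure. This is an inference, but the illustrated gain is sensitive to it. Extending the nadir range to day 28 cuts the gain for 6-day episodes to about 2 to 8 points. Extending it to day 31 leaves about 0 to 2 points for 6-day and 0 to 4 points for 10-day episodes. This stands as a caution on size. It does not reverse the conclusion: the average gain stays at about zero or above, and days 10 to 25 is the range the protocol states.

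**A count outside the range need not miss a low count.** In the same model, draws on days 7 and 28 see no 6-day episodes but 27% of 10-day and 53% of 14-day episodes. After the cap, days 7 and 25 are still permitted, leave days 8 to 24 unsampled and catch only 20% of 6-day episodes. This is correct: the cap guarantees one count in the range and no more.

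**No harm is shown.** The declines are described as moderate and mostly not clinically significant. The febrile neutropenia and leucopenia dose-limiting toxicities cited were at 200 and 250 mg, while "Part A defined the MTD in the patient population who participated as 175 mg daily", which is the dose used here. Febrile neutropenia and hospitalization trigger action separately. The readable text does not allow the number of missed episodes to be estimated. All of this stands and keeps the point minor.

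**The 6-day rule needs serial counts**, which this change does not supply. That also stands.

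**There is a trade-off.** Under the two readings that start earlier, nadirs on days 23 to 25 are caught less often:
- Days 12 to 31: 32% to 31% (6-day episodes), 53% to 46% (10-day) and 72% to 62% (14-day).
- Days 15 to 28: 46% to 40%, 69% to 60% and 85% to 80%.

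Averaged over the whole nadir range, detection still rises under every reading and episode length tried.

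**Conclusion.** The concern holds as a minor point. That a compliant patient can have no count in days 10 to 25 follows from the protocol's own text under every reading of the week labels tried, and a firm limit at day 25 removes the possibility. This part needs no distributional assumption. How many more episodes would be seen does: the gains in the table depend on assumed nadir, draw-day and episode-length distributions, and they shrink towards zero if nadirs extend well beyond day 25. The clinical consequence is probably small. Confidence in the overall importance is medium.

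**What to change.** In section 3.4 and Appendix A, require the blood draw of the existing week 3-4 visit no later than day 25 after the first dose. No tolerance should be added beyond day 25, and the earliest permitted day should stay as it is (for example days 15 to 25 if week 3-4 means days 15 to 28). Apply the limit to randomized patients and to cross-over patients starting saracatinib. The thoracic CT at that visit is there to monitor for interstitial lung disease and can keep its present window.

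The cost is a wording change, with no new visit or test. Scheduling becomes slightly less flexible, and some patients may have blood drawn on a different day from the CT, which could mean an extra trip; local evaluation is already permitted for this visit. A further count near day 14 would cover more of the range, but it would add a test and is not needed to close the stated gap.
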